### 7.4 Statistical Analyses of the Exploratory Objectives

(a) Rates of ki-67 at core biopsy and 5-7 weeks post-RT will be estimated with 95% CI's.

(b) The analysis of the impact of radiation on gene expression is described in Appendix 1.

(c) To review treatment plans, evaluate delivery techniques and assess positioning verification images

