##### **Exploratory Objectives**

1. Ki-67 will be assessed as a measure of tumor response.
2. Assess the impact of radiation on gene expression
3. Assess the impact of radiation on circulating cell-free DNA via serum markers and oxidative stress as measured by urinary biomarkers. Please see Appendix VI for additional detail regarding serum and urine assessment.
4. To review treatment plans, evaluate delivery techniques and assess positioning verification images

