### **5. TREATMENT PLAN**

#### **5.1 Surgery:**

Surgical tumor resection will be completed within 10 days of RT delivery. Subjects will undergo intraoperative lymphatic mapping and sentinel lymphadenectomy as is standard at our institution. Standard axillary nodal dissection is acceptable if there is a contraindication to the sentinel node procedure or if felt to be clinically indicated based on nodal involvement. Omission of nodal assessment is also acceptable if clinically indicated and will not be performed in patient's diagnosed with DCIS. Resection of the tumor will include a 2mm margin of normal tissue. In general, re-excision is required for histologic margins <2mm. There may be exceptions, however, when a close margin occurs at an anatomic boundary (typically chest wall/skin) or is nearly 2mm or only focally close. Those margins are generally felt to be less significant prognostically and the role for re-excision in these cases will be made by the treating surgeon and radiation oncologist. Typically, surgical clips marking the site of tumor excision will be placed to allow for localization of the tumor bed on follow-up imaging. Standard pathologic assessment will follow.

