#### **Post-operative Treatment:**

Within 10 days, subjects will proceed to surgical resection. Pathologic assessment will be completed and reviewed per standard of care. Ki-67 will be assessed on core biopsy and definitive resection tumor (as per institutional standard) as a measure of tumor response.

Systemic therapy will only be delivered if indicated. The role for adjuvant radiation will be discussed for any patient whose pathologic assessment reveals an unanticipated high risk feature. Features judged by the multi-disciplinary treatment team to be of comparable clinical risk relative to the presenting

diagnosis (ex. a 1.8cm tumor on imaging that is just over 2cm at resection) will not necessarily require post-operative radiation. Additional radiation will be recommended to individual patients whose locoregional extent of disease is significantly greater than expected at the time of surgery (ex. nodal involvement).

Treatment volumes and prescribed doses will follow institutional standards. Hypofractionated breast treatment will be considered an acceptable alternative to standard therapy (46-50Gy) when clinically appropriate.

Subjects requiring mastectomy will be included in the correlative portion of the trial. However, their cosmesis, recurrence and late RT toxicities outcomes will be gathered and recorded separately. It would not be accurate to compare the secondary endpoints of these subjects to those receiving breast conservation.

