## 6. PATIENT ASSESSMENTS

Assessment	Pre-Tx.	Follow-up
Consent	X	
History/Physical	X	X a
Complete Blood Count (no differential)/CMP	X	
Breast imaging (mammogram minimum)	X	X a
Core Biopsy/Fiducial Markers	X b	
Planning MRI	X	
Surgical Excision with Tissue Procurement		X c
Acute Toxicity Evaluation		X d
Cosmetic Evaluation Form/Digital Photographs/QOL	X e	X e
Clinical Outcomes		X a
Serum collection	X f	X f
Urine collection	X g	X g
BRPC Consent prior to surgery		X h

- a. Physical exam by member of oncology team recommended every 4-6 months for 2 years, every 6 months through year 5 and annually years 5-10. Bilateral mammogram recommended at least annually.
- b. Verify placement of a biopsy clip at diagnostic procedure and availability of pre-treatment tissue for correlative science.
- c. Within 10 days of radiation.
- d. Appointment with the Radiation Oncologist/mid level provider 1-2 months after surgery.
- e. At baseline (prior to treatment), six months and one year after treatment and then annually for 2 additional years. Cosmetic assessment to be filled out by both patient and physician/mid level provider. Digital photographs at the same time points and at investigator's discretion.
- f. 2 lavender tubes drawn prior to radiation therapy and post radiation therapy (before surgery)
- g. Urine collected prior to radiation therapy and post radiation therapy (before surgery)
- h. Subjects will be consented to the existing Biospecimen Repository and Processing Core (BRPC) tissue collection protocol which includes safeguards to ensure adequate tissue for diagnostic evaluation and biomarker assessment

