### **6.3 Treatment Period:**

Lumpectomy will be completed within 10 days of RT delivery. Tissue will be processed as described below in section 8.1. A second biopsy will be collected for gene expression profiling as described in Appendix 1. After preoperative treatment, the patient will be assessed 1-2 months after surgery by a Radiation Oncology faculty member/mid level provider to evaluate for acute toxicity. Subjects will go on to systemic therapy or conventional radiation if a high risk feature not anticipated pre-operatively is noted at the time of surgery. If indicated, subjects will be seen weekly during conventional treatment as is standard procedure in our department. .

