## 11. APPENDICES

### APPENDIX I: Tissue Studies

Tissue collected pre and post treatment will be used to explore the biologic response to radiotherapy by comparing changes in gene expression pre and post-radiotherapy:

- a. Assess changes in gene expression following radiation.  
Formalin-fixed paraffin-embedded tissue will be utilized for harvesting of RNA. Gene expression will be assessed using the Affymetrix HTA arrays designed for FFPE samples. We have previously successfully used an FFPE Affymetrix platform on our phase I FFPE samples.
- b. Ki-67 will be assessed in the pre and post radiotherapy tissue samples

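### Section 7.4(a) sets the post-radiation Ki-67 time point at 5-7 weeks, which no patient on the current surgery schedule can supply, and plans no within-patient change

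*Combined protocol and SAP*

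**What the plan says.** The exploratory objectives in section 3.1 give Ki-67 its purpose: "Ki-67 will be assessed as a measure of tumor response". The only analysis text for it is section 7.4(a): "Rates of ki-67 at core biopsy and 5-7 weeks post-RT will be estimated with 95% CI's".

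The specimens are defined elsewhere. Under Post-operative Treatment in section 5.2: "Ki-67 will be assessed on core biopsy and definitive resection tumor (as per institutional standard) as a measure of tumor response". Appendix I adds: "Ki-67 will be assessed in the pre and post radiotherapy tissue samples".

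The timing of resection is given consistently in the current text. Section 5.1: "Surgical tumor resection will be completed within 10 days of RT delivery". Section 6.3: "Lumpectomy will be completed within 10 days of RT delivery". Footnote c to the section 6 assessment table, attached to surgical excision with tissue procurement: "Within 10 days of radiation". Post-operative Treatment in section 5.2 repeats the 10-day limit.

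Sections 7.1 and 8 explain the history. Surgery had been done about 6 weeks after radiation, more wound-healing problems and seromas were seen, and an amendment returned surgery to within 10 days. Section 8 says that an interim analysis covered the first 17 patients.

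**The concern.** Section 7.4(a) is live analysis text, but its second time point belongs to the old schedule. An analyst who follows it has no qualifying post-radiation value for any patient treated under the current schedule. An analyst who departs from it and uses every resection specimen combines tumours removed at about 6 weeks with tumours removed within 10 days. Because the schedule changed by amendment, that interval is also tied to enrolment period. The plan does not say which reading applies, so the choice would be made once the data are in hand.

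The second problem is the estimator. Both specimens come from the same patient, and the stated purpose is response, which is a change from before to after. The plan gives one estimate before and one after, and nothing for the difference between them.

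**Working it through.** The documents state no sample size, power or precision figure for Ki-67, so there is no figure to reproduce. The check is a comparison of dates and specimens, followed by a short calculation on what two marginal intervals can and cannot show.

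**1. Window against surgery**

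| Item | Source | Days after radiation |
|---|---|---|
| Second Ki-67 time point | 7.4(a) | 5 × 7 = 35 to 7 × 7 = 49 |
| Last permitted day of resection | 5.1, 5.2, 6 (footnote c), 6.3 | 10 |
| Gap | 35 − 10 | at least 25 |

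**2. Is there any other tissue in the window?** Section 5.2 names only the core biopsy and the definitive resection for Ki-67. Section 6.3 mentions a second biopsy, but for gene expression, and Appendix I obtains that second sample at resection. No section schedules tissue collection at 5-7 weeks.

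**3. Who could have a 5-7 week sample?** Only patients operated on under the 6-week schedule. Their number is not stated. The 17 in section 8 is the size of the interim analysis, not a count of 6-week operations. The original target in section 7.1 was 40 and the current target is 100. As an illustration only, assume that 17 to 40 patients had surgery on the earlier schedule and that all 100 are enrolled. Then 100 − 40 = 60 to 100 − 17 = 83 patients would have no sample in the window.

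**4. What two marginal intervals leave out.** For a continuous Ki-67 value,

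Var(change) = Var(before) + Var(after) − 2 Cov(before, after),

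and the covariance cannot be recovered from two separate CIs. The same holds for a proportion above a cut-off. With p10 the proportion of patients moving from above to below the cut-off and p01 the reverse, the 95% half-width for the paired difference is

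1.96 × √{[p10 + p01 − (p10 − p01)²] / n}.

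Take assumed values of 50% before, 30% after, and n = 100. The marginal half-widths are fixed at 1.96 × √(0.5 × 0.5/100) = 0.098 and 1.96 × √(0.3 × 0.7/100) = 0.090. The half-width for the change is not fixed:

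| p01 | p10 | Half-width of paired change |
|---|---|---|
| 0.00 | 0.20 | 0.078 |
| 0.05 | 0.25 | 0.100 |
| 0.15 (before and after unrelated) | 0.35 | 0.133 |

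The same two marginal results are thus compatible with quite different precision for the change. The percentages and n are assumptions; the documents give no Ki-67 rate, SD, cut-off or correlation.

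**5. Is a paired analysis given elsewhere?** Appendix I speaks of comparing changes before and after radiation for gene expression. For Ki-67 it says only that both samples will be assessed. No section specifies a paired difference or test for Ki-67.

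**The case against.** The strongest reply is that this is a stale label in one exploratory sentence. Section 5.2 identifies the post-radiation specimen by its source, so the right tissue is being collected and a sensible analyst would use it. That stands, and it limits the harm. It does not settle how to handle patients from the two schedules, which the plan leaves open.

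It can also be said that separate estimates with 95% CIs match the descriptive style of section 7.3(a) and (b), that the 10/01/2025 amendment in section 3.3 D makes Ki-67 hypothesis-generating, and that nothing prevents a paired summary from the same data. This is fair. The missing paired change is the weaker half of the point: a mismatch with the stated purpose rather than an error that blocks the analysis.

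Three stronger readings are tempting, and the documents support none of them.

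- A reader might infer that the 5-7 week sample exists for nobody. Patients operated on under the earlier schedule can have one.
- A reader might infer that usable values fall from 100 to 17. Neither end is established: 17 is only the interim count, 100 is a ceiling, and section 3.3 D itself cites small numbers and scarce tissue.
- A reader might put a figure on the precision lost by not pairing, using the ratio √(1 − r) of paired to independent-sample interval width. The arithmetic is correct for a continuous measure with equal variances, but section 7.4(a) proposes no independent-sample difference to compare with, and r is not given.

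**Conclusion.** The point holds. The second time point in section 7.4(a) cannot be met by any patient on the current schedule and contradicts the specimen definition in section 5.2; the passages must be reconciled. The two marginal estimates do not deliver an interval for the change that the objective calls for.

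The conclusion on timing rests on the text alone. Its numerical reach does not: the number of 6-week-schedule patients is unstated, so the 60 to 83 above is an assumed range, and the benefit of pairing cannot be quantified.

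The impact is limited. Ki-67 is exploratory and drives no decision, monitoring rule or sample size. The primary cosmesis endpoint and the secondary endpoints are untouched. The correction is worth making because it is cheap and because, with little tissue available, the pairs that exist should be used well.

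**What to change.** Revise section 7.4(a) to agree with section 5.2:

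1. Replace the 5-7 week time point with the definitive resection specimen.
2. State what a Ki-67 rate is: percent positive cells, or the proportion of patients above a named cut-off. The form of the paired interval depends on this (mean or median change for the first, a difference in paired proportions for the second).
3. Keep the two marginal estimates and add the within-patient change from core biopsy to resection with a paired 95% CI, giving the number of pairs.
4. Present patients from the 6-week schedule separately, or account for the radiation-to-surgery interval in the analysis. State their number.

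The cost is a few sentences of analysis text. It needs no new samples or procedures, and nothing here proposes a change to the timing of surgery.

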## 8. SAFETY MONITORING AND REPORTING

The PI is responsible for the identification and documentation of adverse events and serious adverse events, as defined below. At each study visit, the PI or designee must assess, through non-suggestive inquiries of the subject or evaluation of study assessments, whether an AE or SAE has occurred.

Previously, an interim analysis of the first 17 patients was completed. Delayed wound healing, and an increase in grade 2 seromas, relative to our Phase I experience, were observed. The PI and study team believe that there is an interaction between the radiation and surgery (when completed 6 weeks after protocol treatment) that was not seen with our previous practice of 10 days after protocol treatment. Therefore, with the current amendment, we are returning to the practice established from our phase 1 study (Pro00015617) where minimal toxicities were observed. Whilst adverse events will continue to be monitored vigorously, it is not anticipated that those toxicities will be seen in future enrolled subjects given our prior experience. Therefore, there is no plan to complete an additional interim analysis for this study.

### 8.1 Adverse Events:

An adverse event (AE) is any untoward medical occurrence in a subject receiving study therapy and which does not necessarily have a causal relationship with this treatment. For this protocol, the definition of AE also includes worsening of any pre-existing medical condition. An AE can therefore be any unfavorable and unintended or worsening sign (including an abnormal laboratory finding), symptom, or disease temporally associated with the use of radiation therapy, whether or not related to use of the radiation therapy. Abnormal laboratory findings without clinical significance (based on the

PI's judgment) should not be recorded as AEs. But laboratory value changes that require therapy or adjustment in prior therapy are considered adverse events.

From the time the subject signs the informed consent form through the End of Study visit, all AEs must be recorded in the subject medical record and adverse events case report form.

AEs will be assessed according to the CTCAE version 4.0. If CTCAE grading does not exist for an AE, the severity of the AE will be graded as mild (1), moderate (2), severe (3), life-threatening (4), or fatal (5).

Attribution of AEs will be indicated as follows:

- Definite: The AE is clearly related to the study therapy
- Probably: The AE is likely related to the study therapy
- Possible: The AE may be related to the study therapy
- Unlikely: The AE is doubtfully related to the study therapy
- Unrelated: The AE is clearly NOT related to the study therapy

#### **8.1.1 AEs of Special Interest**

All possible treatment related adverse events/toxicities reported or observed, the information should be recorded in the patient's medical record and on the study's Toxicity Evaluation Form or in the study's toxicity database. This should include a description of the event, its severity grade, the relationship to the study treatment and the onset date.

#### **8.1.2 Reporting of AEs**

All grade 4 or higher unexpected and possibly related toxicity will be reviewed by the PI and study team and reported to the Duke University Health System IRB via the eIRB system.

#### **8.2 Serious Adverse Events:**

An AE is considered "serious" if in the opinion of the investigator it is one of the following outcomes:

- Fatal
- Life-threatening
- Constitutes a congenital anomaly or birth defect
- A medically significant condition (defined as an event that compromises subject safety or may require medical or surgical intervention to prevent one of the three outcomes above)
- Requires inpatient hospitalization or prolongation of existing hospitalization
- Results in persistent or significant incapacity or substantial disruption to conduct normal life functions

#### **8.3 Safety Oversight Committee (SOC):**

The Duke Cancer Institute SOC is responsible for annual data and safety monitoring of DUHS sponsor-investigator phase I and II, therapeutic interventional studies that do not have an independent Data Safety Monitoring Board (DSMB). The primary focus of the SOC is review of safety data, toxicities and new information that may affect subject safety or efficacy. Annual safety reviews includes but may not be limited to review of safety data, enrollment status, stopping rules if applicable, accrual, toxicities, reference literature, and interim analyses as provided by the sponsor-investigator. The SOC in concert with the DCI Monitoring Team (see Section 12.1 for Monitoring Team description) oversees the conduct of DUHS cancer-related, sponsor-investigator greater-than-minimal-risk intervention studies that do not have an external monitoring plan, ensuring subject safety and that the protocol is conducted, recorded and reported in accordance with the protocol, standing operating procedures (SOPs), Good Clinical

Practice (GCP), and applicable regulatory requirements. The DCI Safety Oversight Committee (SOC) will perform annual reviews on findings from the DCI Monitoring Team visit and additional safety and toxicity data submitted by the Principal Investigator.

## **9. QUALITY CONTROL AND QUALITY ASSURANCE**

### **9.1 Monitoring:**

This clinical research study will be monitored both internally by the PI and institutionally by the Duke Cancer Institute (DCI). In terms of internal review the PI will continuously monitor and tabulate adverse events. Appropriate reporting to the Duke University Medical Center IRB will be made. If an unexpected frequency of Grade III or IV events occur, depending on their nature, action appropriate to the nature and frequency of these adverse events will be taken. This may require a protocol amendment, dose de-escalation, or potentially closure of the study. The PI of this study will also continuously monitor the conduct, data, and safety of this study to ensure that:

Stopping rules for toxicity and/or response are met;

Risk/benefit ratio is not altered to the detriment of the subjects;

Appropriate internal monitoring of AEs and outcomes is done;

Over-accrual does not occur;

Under-accrual is addressed with appropriate amendments or actions;

Data are being appropriately collected in a reasonably timely manner.

DCI review and monitoring of this protocol occurs in accordance with the NCI-approved Data and Safety Monitoring Plan. Briefly, protocol review begins with an initial review by the Cancer Protocol Committee (CPC), which assesses the ethics and safety of the protocol. Documentation of these assessments will be maintained. Formal, independent monitoring will be conducted by the DCI Monitoring Team after the first 3 subjects are enrolled, followed by annual monitoring of 1-3 subjects until the study is closed to enrollment and subjects are no longer receiving study interventions that are more than minimal risk. DCI Monitoring Team reports and additional data/safety/toxicity reports submitted by the PI will be reviewed by the Safety Oversight Committee (SOC) on an annual basis. Additional monitoring may be prompted by findings from monitoring visits, unexpected frequency of serious and/or unexpected toxicities, or other concerns. Monitoring visits may also be initiated upon request by DUHS and DCI Leadership, CPC, SOC, a sponsor, an investigator, or the IRB.

### **9.2 Audits:**

The Duke School of Medicine Clinical Trials Quality Assurance (CTQA) office may conduct confidential audits to evaluate compliance with the protocol and the principles of GCP. The PI agrees to allow the CTQA auditor(s) direct access to all relevant documents and to allocate his/her

time and the time of the study team to the CTQA auditor(s) in order to discuss findings and any relevant issues.

CTQA audits are designed to protect the rights and well-being of human research subjects. CTQA audits may be routine or directed (for cause). Routine audits are selected based upon risk metrics generally geared towards high subject enrollment, studies with limited oversight or monitoring, Investigator initiated Investigational Drugs or Devices, federally-funded studies, high degree of risk (based upon adverse events, type of study, or vulnerable populations), Phase I studies, or studies that involve Medicare populations. Directed audits occur at the directive of the IRB or an authorized Institutional Official.

CTQA audits examine research studies/clinical trials methodology, processes and systems to assess whether the research is conducted according to the protocol approved by the DUHS IRB. The primary purpose of the audit/review is to verify that the standards for safety of human subjects in clinical trials and the quality of data produced by the clinical trial research are met. The audit/review will serve as a quality assurance measure, internal to the institution. Additional goals of such audits are to detect both random and systemic errors occurring during the conduct of clinical research and to emphasize “best practices” in the research/clinical trials environment.

